2.8 Correlative laboratory samples

The study will not collect correlative laboratory samples. However, the unique clinical data from this study forms a rich dataset for future exploration of correlative samples. Therefore, we will encourage the study team to offer the CIBMTR “Protocol for a Research Sample Repository for Allogeneic Hematopoietic Stem Cell Transplantation, Other Cellular Therapies and Marrow Toxic Injuries.” to patients.

CHAPTER 3

3 STUDY ENDPOINTS

3.1 Primary Endpoint

NRM is defined as death without relapse or progression of the primary hematologic malignancy within the first year of allogeneic transplantation. Relapse will be considered a competing risk and will be defined as per the CIBMTR definition for each hematologic malignancy.

3.2 Secondary Endpoints

3.2.1 Overall survival within 1 year

Overall survival is defined as death from any cause within 1 year of transplant. Surviving subjects will be censored at the date of last follow-up.

3.2.2 Development/Progression of Frailty (DPF)

Frailty will be measured at baseline, day 100, day 180 and day 365 by the 5 component Hopkins frailty phenotype (5 points total, score of 3 or more is frail). Of note, weight loss at day 100, day 180 and 365 will be scored from the prior time point for the purposes of this study rather than 1 year weight loss. DPF at 1 year is defined as an increase to a score of 3 or more (i.e., frail) in subjects who are not frail at baseline, or an increase in the frailty score of one or more points in those who are already frail at baseline. Subjects who miss assessments will be considered censored at the date of last follow-up. Death prior to development/progression of frailty will be considered a competing risk.

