2.4.8 Physical Frailty Phenotype

We will measure frailty using the Hopkins Frailty Phenotype instrument, developed by Fried²⁹ in the Cardiovascular Health Study, and validated by Bandeen-Roche and colleagues⁵³ in the Women's Health and Aging Studies at baseline, day 100, day 180 and day 365. The frailty assessment includes 5 core criteria: 1) measured walking speed; 2) measured grip strength; 3) an exhaustion questionnaire; 4) a physical activity questionnaire; and 5) questions about unintentional weight loss / low body mass index (BMI).

Necessary tools to measure frailty include the following equipment:

- Scale (preferably physician/medical scale) for weight measurement
- Stadiometer (preferably wall-mounted) or other height measurement tool
- Dynamometer (grip strength measurement tool, by Jamar, provided by the study)
- Stopwatch (To time walking speed measurement)
- Tape Measure (To lay out 4-meter walking course for Walking Speed Measurement)

Subject reported Frailty Phenotype: Standardized self-reported questionnaires will be used to capture exhaustion, physical activity, and weight loss as shown in **Appendix 4**. Weight loss pre-transplant reflects the prior year. Weight loss at day 100 and day 180 will be asked for the prior 3 months to reflect time since the prior assessment. At day 365, weight loss will be asked over the prior 6 months.

Health Care Team Frailty Phenotype: Grip strength and 4-meter walk are both measured by the healthcare team. The 4-meter walk is measured at comfortable pace in a normal hallway on a marked course and recorded using stopwatch (2 trials). Grip strength is recorded using a handheld Jamar dynamometer (3 trials). The dynamometer will be provided by the study. Weight and height are also measured.

Scoring: Scoring will be performed centrally following the algorithm from the Hopkins Frailty Assessment Calculator (<http://hopkinsfrailtyassessment.org/>) to determine a participant's frailty status. In brief, a 5 point score is generated from each core criteria. Frail (1 point) or not frail (0 points) is assigned for each core criteria. A score of 1-2, or 3-5 results in classification as pre-frail or frail, respectively. Walk speed will also be used as predictor variable at baseline using a threshold different from the frailty index (Table 5.9.1).

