5.6 Demographic and Baseline Characteristics

Demographics and baseline characteristics will be summarized for all subjects. In addition to the variables being utilized for the risk score development in Table 5.9.1, other characteristics to be examined are: age, gender, race/ethnicity, primary disease, disease-specific risk categories per Disease-risk index (DRI), donor type and HLA matching, stem cell source, donor/recipient CMV status, donor/recipient sex match, and intensity of conditioning regimen.

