5.8.2 Development/Progression of Frailty (DPF)

Frailty will be summarized at each time point using descriptive statistics. Incidence of DPF up to 1 year will be estimated with 95% confidence intervals using the cumulative incidence estimate, treating death prior to DPF as a competing event. A multivariate Cox regression model for the cause-specific hazard of DPF will be fit to estimate hazard ratios of the CHARM risks groups after adjustment for baseline characteristics as described above. Additionally, we will develop a separate Cox model using individual predictors rather than the overall CHARM score in order to assess the relative importance of the predictors in Table 5.9.1 on DPF and compare to CHARM predictive power for DPF.

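### The frailty endpoint needs a different amount of change at each baseline score, but the model comparing CHARM groups leaves that score out

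*Protocol*

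**What the plan says.** Section 3.2.2 defines development/progression of frailty (DPF) in two parts. For subjects scoring 0–2 at baseline it is "an increase to a score of 3 or more (i.e., frail) in subjects who are not frail at baseline". For those scoring 3–5 it is "an increase in the frailty score of one or more points in those who are already frail at baseline". Section 2.4.8 supplies the categories: "A score of 1-2, or 3-5 results in classification as pre-frail or frail, respectively". On timing, "Frailty will be measured at baseline, day 100, day 180 and day 365 by the 5 component Hopkins frailty phenotype", so there are three assessments at which an event can be recorded.

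Section 5.8.2 gives the analysis: "Incidence of DPF up to 1 year will be estimated with 95% confidence intervals using the cumulative incidence estimate", with death as a competing event. Then: "A multivariate Cox regression model for the cause-specific hazard of DPF will be fit to estimate hazard ratios of the CHARM risks groups". This model is adjusted, and the adjustment set is described at the start of section 5.8, where covariates are chosen stepwise from the characteristics in section 5.6. Section 5.6 opens with "In addition to the variables being utilized for the risk score development in Table 5.9.1, other characteristics to be examined are" and goes on to list demographic, disease, donor and transplant variables.

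**The concern.** The event is not the same event for everyone. One criterion turning positive is enough from score 2, while three are needed from score 0. A subject at 5 cannot have the event at all, yet nothing removes that subject from the risk set. If CHARM is related to the baseline score, CHARM groups start at different distances from the event, and the hazard ratio mixes that difference with any difference in later change.

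This matters because sections 2.2.1 and 5.1 put the hypothesis in terms of frailty trajectories after transplant. From the planned hazard ratio alone, a reader could not tell whether CHARM predicts decline or identifies who begins next to the threshold.

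**Working it through.** **Step 1. Points needed for an event (section 3.2.2).** For baseline scores 0–2 the distance is 3 minus the score: 3, 2 and 1 points. For scores 3 and 4 it is 1 point. For score 5 it is unreachable, since the scale ends at 5.

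**Step 2. Is the baseline score in the model?** Section 5.6 does not name the frailty score or category. If its opening clause also makes the Table 5.9.1 variables eligible, the score is still not recovered. Grip strength, exhaustion and activity are absent from that table. Walk speed and weight loss appear there with other cut points: 0.8 m/s and 10%, against 0.65/0.76 m/s and 5% in Appendix 3.1.

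**Step 3. Is CHARM likely to track baseline frailty?** Table 5.9.1 takes walk speed and weight loss from the frailty phenotype (two of its five criteria) and adds IADL, PROMIS Physical Function and self-rated KPS. A positive correlation is likely but not certain, because stepwise selection has yet to fix what CHARM contains.

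**Step 4. How large could the effect be?** The protocol states no DPF rate, no reliability for the frailty score, no distribution over 0–5 and no CHARM–frailty correlation, so it has no figure of its own to reproduce here. Its sample-size sum (12 × 16 / 0.22 = 872.7, stated as 880) concerns non-relapse mortality only.

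The following is therefore assumed. There are 400,000 subjects with no true change in frailty. Five binary criteria share one latent factor (squared loading 0.3), calibrated to 25% frail at baseline, which is about the share section 1.6.2 cites from an earlier series aged 50 and over. Each criterion is misclassified with probability e at each visit. There are three follow-up visits and no death or dropout. A CHARM proxy with correlation r to latent frailty is cut into tertiles and analysed in a grouped-time complementary log-log model.

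At e = 5%:

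| Baseline score | Share of subjects | Noise-only DPF | Share × risk |
|---|---|---|---|
| 0 | 22.7% | 0.6% | 0.14% |
| 1 | 29.0% | 5.4% | 1.57% |
| 2 | 23.4% | 32.6% | 7.63% |
| 3 | 15.0% | 25.6% | 3.84% |
| 4 | 7.6% | 16.1% | 1.22% |
| 5 | 2.4% | 0% | 0% |

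The last column sums to 14.4%. Score 2 supplies 7.63 / 14.4 = 53% of these events.

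Top-versus-bottom tertile hazard ratio, without → with baseline score in the model:

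| e | r = 0.3 | r = 0.5 | r = 0.7 |
|---|---|---|---|
| 2% | 1.52 → 1.13 | 2.05 → 1.23 | 2.91 → 1.35 |
| 5% | 1.49 → 1.17 | 2.02 → 1.35 | 2.84 → 1.58 |
| 10% | 1.46 → 1.28 | 1.94 → 1.56 | 2.63 → 1.96 |
| 15% | 1.39 → 1.34 | 1.76 → 1.66 | 2.26 → 2.13 |

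At r = 0 the ratio is about 1.0 with or without the score. In the central case (e = 5%, r = 0.5) adjustment removes 1 − ln 1.35 / ln 2.02 = 57% of the log hazard ratio. At e = 15% and r = 0.5 it removes only 1 − ln 1.66 / ln 1.76 = 10%, because a noisy baseline score is a poor control for true frailty.

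**Step 5. Would confirmation help?** Over e = 2–15%, requiring two consecutive qualifying visits cuts noise-only incidence from 6.9–29.1% to 1.7–7.1%. In the central case the bottom and top tertile rates go from 9.8% and 18.8% (ratio 1.9) to 2.0% and 5.8% (ratio 2.9). Incidence falls, but the relative gradient does not.

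**The case against.** The strongest reply is that CHARM is a prediction score. Section 2.2.3 asks whether it predicts the cumulative incidence of frailty, and poor baseline function is part of what it is meant to capture. Adjusting for the baseline score answers a narrower question. This stands, and it is why the planned hazard ratio should remain. It does not dispose of the trajectory hypothesis in sections 2.2.1 and 5.1.

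The threshold of 3 is also the instrument's own frail category, so entering it is a natural definition of development and is not an error. Section 5.8.2 already plans frailty summaries at each visit and a separate model with individual predictors. Those help, but neither conditions on the baseline score. An analysis plan not shown here may add such a model, but the protocol fixes the adjustment set without it.

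Some features work against spurious events. Weight loss is scored over a shorter period after baseline (section 3.2.2), and grip strength is omitted at remote visits (Appendix 3.3). Walk speed is averaged over two trials, the best of three grip trials is used, and assessor training is mandatory.

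A reader might infer more: that measurement noise alone would pile events into the high-CHARM group and yield a large hazard ratio, say above 3. The documents do not support that. They give neither an error rate nor a correlation, no combination in the working exceeds 2.91, and with no correlation there is no gradient. Noise risk also peaks at score 2 and falls to zero at 5, so the frailest subjects are not the most exposed.

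**Conclusion.** The point holds as a matter of interpretation for one secondary endpoint; the primary endpoint is untouched. The unequal distance to the event, the absence of the baseline score from the stated adjustment set, and the retention of score-5 subjects all follow from the text. That CHARM correlates with baseline frailty is a reasonable expectation, not a stated fact.

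The size depends on the assumptions: a top-versus-bottom hazard ratio of about 1.4–2.9 with no true change over the ranges tried, about 2.0 in the central case, and about 1.0 with no correlation. Including the baseline score reduces the artefact without removing it, to 1.13–2.13 over the same ranges. The score-5 issue is minor in number: at the simulated 2.4%, about 0.024 × 880 = 21 subjects. Keeping them slightly understates incidence among those who can have the event.

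**What to change.** Keep the definition in section 3.2.2 and the planned CHARM analysis. In section 5.8.2:

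- also report the CHARM hazard ratio from a Cox model stratified by baseline frailty score (0, 1, 2, 3, 4), beside the planned one;
- exclude subjects with a baseline score of 5 from the DPF risk set, and state how many there are;
- report DPF incidence by baseline frailty category.

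This takes some added wording and one further model on data already collected. The price is a stratified hazard ratio that will be smaller and answers the narrower question, so it should not replace the planned one.

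A sensitivity analysis counting only events also present at the next assessment is optional. It lowers noise-only incidence but not the gradient. It loses events first seen at day 365 and those followed by death before the next visit, which is not negligible when Table 5.9.2 puts one-year survival at 57–63%. Before any day-100 event is counted or confirmed, Table 4.2.4 and the Appendix 4 table need reconciling: the first schedules the self-reported weight-loss, exhaustion and activity items at day 100, and the second does not.

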3.2.3 Development/Progression of Disability

Modified (omitting laundry) Lawton (i.e., OARS) instrumental activities of daily living (IADL) assessment will be measured at baseline, day 100, day 180 and day 365.⁵⁶ Disability is defined as any assistance needed for a specific IADL domain. Development/Progression of Disability will be measured by loss of an additional IADL from baseline (i.e. worsening of disability score by 1 or more IADL) within 1 year. Subjects who miss assessments will be considered censored at the date of last follow-up. Death prior to development/progression of disability will be considered a competing risk.

3.2.4 Facility Admission

Facility admission will include any overnight stay in a skilled nursing facility outside of the hospital. Facilities include rehabilitation, subacute rehabilitation and nursing-homes. Generally, such admissions occur as discharges from the hospital setting. Residing at home with a nurse or paid caregiver would not be considered a facility admission. Transfer of care to a rehabilitation center within the same hospital or organization would also be considered a facility admission for

the purpose of the protocol as this implies the subject was not well enough to live independently. The study chairs should be contacted to reconcile ambiguities.

Facility admission will be measured for the prior 3 months at day 100 and day 180 and the prior 6 months at day 365. The cumulative incidence of first admission to a facility as well as the rate of admissions accounting for recurrent admissions will be calculated over one year.

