2.6.4 Facility Admissions

Subjects will be asked about admission to skilled facilities inclusive of nursing-homes and rehabilitation. This will cover the prior 3 months on days 100 and 180 and the prior 6 months at baseline and day 365.

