4.2.4 Subject Evaluations

Table 4.2.4 summarizes assessments over the course of the study.

Table 4.2.4: Study Assessments

| Study Assessments / Testing | Healthcare Team (H) or Subject Report (P) or Lab (L)* | Baseline (Pre-conditioning) | Day 100 - 14/+21 (abbreviated survey) | Day 180 +/- 28 | Day 365 +/- 28 |
|--|---|-----------------------------|---------------------------------------|----------------|----------------|
| Subject report | | | | | |
| Race/ethnicity, education, income, demographics | P | X | | | |
| Karnofsky performance status (KPS) by subject | P | X | X | X | X |
| PROMIS Physical function domain | P | X | X | X | |
| PROMIS Depression domain | P | X | X | X | X |
| PROMIS Anxiety domain | P | X | X | X | X |
| Facility admissions ³ | P | | X ⁵ | X ⁵ | X ⁵ |
| OARS IADL ¹ | P | X | X | X | X |
| Falls | P | X | X ⁵ | X ⁵ | X ⁵ |
| Frailty phenotype - Weight loss ² | P | X | X ⁵ | X ⁵ | X ⁵ |
| Frailty phenotype - Exhaustion ² | P | X | X | X | X |
| Frailty phenotype- Activity level ² | P | X | X | X | X |
| Number of medications for polypharmacy | P | X | | | |
| Healthcare team report | | | | | |
| Frailty phenotype - Walk Speed, 4 meter ² | H | X | X ⁷ | X ⁷ | X ⁷ |
| Frailty phenotype- Grip Strength ² | H | X | X | X | X |
| Montreal Cognitive Assessment (MoCA) for cognition | H | X | X ⁷ | | |
| CIBMTR Forms | H | X | X | X | X |
| Physician Prognostication Questionnaire | H ⁸ | X | | | |
| Early End of Study Questions (as needed) ⁶ | H | X | | | |
| Laboratory Testing | | | | | |
| CRP ⁴ | L | X | | | |
| Albumin ⁴ | L | X | | | |

*To be performed within 21 days prior to start of conditioning. If multiple values, enter value closest to conditioning.

- 1 OARS IADL 7 questions, omit “laundry” from Lawton IADL
- 2 Fried Frailty phenotype (5 point index). Subject report domains are weight loss, exhaustion and activity level and health care team reports walk speed and grip strength.
- 3 Overnight admission to any facility including nursing-home, subacute rehabilitation
- 4 Standard of care laboratory tests. Must be performed within 14 days prior to start of conditioning.
- 5 The time period for day 100 and day 180 questions will be the prior 3 months and at day 365 the prior 6 months.

- 6 For those who enroll but do not pursue transplantation
- 7 Assessment may be conducted remotely, as described in Appendix 6.3.3. if it is not feasible to conduct the assessment in-person.

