The following table lists all subject reported assessments to be collected, including the number of items and estimated time to complete at each time point. This appendix also includes all items/questions included on each subject reported assessment. For some assessments, language has been modified to fit administration electronically or on paper, as opposed to in person. Any modifications are noted in the below sections.

| Study Assessments / Testing | # of items | Minutes | Baseline (≤21 days Pre-conditioning) | Day 100 -14/+21 | Day 180 +/- 28 | Day 365 +/- 28 |
|---|------------|---------|--------------------------------------|---------------------|----------------------|----------------------|
| Karnofsky performance status by subject | 1 | <1 | X | X | X | X |
| Facility admissions | 1-3 | 1 | | X | X | X |
| PROMIS Depression | 4-12 | 1-2 | X | X | X | X |
| PROMIS Anxiety | 4-12 | 1-2 | X | X | X | X |
| PROMIS Physical function | 4-12 | 1-2 | X | X | X | X |
| OARS IADL | 6 | 2 | X | X | X | X |
| Falls | 1 | <1 | X | X | X | X |
| Frailty phenotype: Weight loss | 2 | <1 | X | | X | X |
| Frailty phenotype: Exhaustion | 5 | 2 | X | | X | X |
| Frailty phenotype: Activity level | 6-18 | 2-5 | X | | X | X |
| Number of medications for polypharmacy | 4 | 1 | X | | | |
| Race/ethnicity, education, income, demographics | 6 | 2 | X | | | |
| Total time for Subject reported outcomes | | | 13-20 minutes | 7-10 minutes | 11-17 minutes | 11-17 minutes |

Race/ethnicity, education, income, demographics

1. What is the highest grade you finished in school?

- 1-8 grades
- 9-11 grades
- High school graduate
- Some post-college work
- Some college
- Junior college degree
- College degree (BA/BS)
- Advanced degree

2. What is your marital status?

- Single, never married

- Married
- Separated
- Divorced
- Widowed

3. What is your current employment status? (please choose all that apply)

- Employed 32 hours a week or more
- Employed less than 32 hours a week
- Full-time student
- Part-time student
- Homemaker
- On medical leave
- Disabled
- Unemployed
- Retired
- Other

4. What is your race? (please select all that apply)

- White
- Asian
- Black or African-American
- Native Hawaiian or Other Pacific Islander
- Native Indian or Alaskan Native
- Don't know

5. What is your ethnicity?

- Hispanic or Latino
- Not Hispanic or Latino
- Don't know

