 - with some help (*can do light housework but need help with heavy work*); or
 - are you completely unable to do any housework?
6. Can you take your own medicines...
- Without help (*in the right doses at the right time*);
 - With some help (*able to take medicine if someone prepares it for you and/or reminds you to take it*); or
 - Are you completely unable to take your medicines?
7. Can you handle your own money...
- Without help (*write checks, pay bills, etc.*);
 - With some help (*manage day-to-day buying but need help managing your checkbook and paying your bills*); or
 - Are you completely unable to handle money?

Falls in past 6 months

Question has been modified from text box, to multiple choice response in order to control data entry in electronic format.

1. How many times have you fallen in the last 6 months?
- 0 times
 - 1 time
 - 2 times
 - 3 or more times

Facility admissions

At day 100 and 180

1. Have you been admitted to a skilled nursing facility in the last 3 months? This would include an acute rehabilitation facility, nursing-home, or sub-acute rehabilitation. Do NOT include admissions to the hospital.

- Yes
- No
- unsure

At day 365

1. Have you been admitted to a skilled nursing facility in the last 6 months? This would include an acute rehabilitation facility, nursing-home, or sub-acute rehabilitation. Do NOT include admissions to the hospital.

- Yes
- No
- unsure

Frailty phenotype: Weight loss*

Questions have been modified for electronic and paper administration during which patient may not be able to self-weigh or recall exact previous weights. Also modified to remove “Refused” response item, as patients may skip question to refuse.

At Pre-HCT

1. To the best of your knowledge, have you lost or gained weight over the past year?

- Yes
- No
- Don't know

2. [if yes] Did you lose or gain weight because you were trying to, or not (For example, by dieting or exercising)?

- Tried to
- Did not try to
- Don't know

Frailty phenotype: Exhaustion*

Questions have been modified to remove “Refused” response item, as patients may skip question to refuse.

* <https://www.johnshopkinssolutions.com/solution/frailty/>

* <https://www.johnshopkinssolutions.com/solution/frailty/>

1. In the past month, on average have you been feeling unusually tired during the day?

- Yes
- No
- Don't know

2. If yes, have you been feeling unusually tired:

- All of the time
- Most of the time
- Some of the time
- Don't know

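### The facility-admission item does not tell subjects how to report a same-hospital rehabilitation stay, which Section 3.2.4 counts as an event although its opening sentence points the other way

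*Protocol*

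**What the plan says.** Section 3.2.4 opens with: "Facility admission will include any overnight stay in a skilled nursing facility outside of the hospital". A few sentences later it extends the endpoint: "Transfer of care to a rehabilitation center within the same hospital or organization would also be considered a facility admission". The reason given is that such a transfer shows the subject could not yet live independently. Ambiguous cases go to the study chairs.

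On collection, Section 2.6.4 says: "Subjects will be asked about admission to skilled facilities inclusive of nursing-homes and rehabilitation". Table 4.2.4 marks facility admissions as subject report at days 100, 180 and 365, with no healthcare-team row. Its footnote 3 reads: "Overnight admission to any facility including nursing-home, subacute rehabilitation".

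The question printed in Appendix 4 (Section 6.4) asks whether the subject was admitted to a skilled nursing facility in the last 3 months (days 100 and 180) or 6 months (day 365). It continues: "This would include an acute rehabilitation facility, nursing-home, or sub-acute rehabilitation. Do NOT include admissions to the hospital". The answers offered are yes, no and unsure.

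**The concern.** An endpoint can be no better than the question that feeds it. Section 3.2.4 deliberately includes a transfer that never takes the subject out of the hospital organisation. The question ends by telling subjects to leave out hospital admissions and does not mention this case. A subject moved from the transplant ward to the same hospital's rehabilitation unit may see this as one continuous hospital stay and answer no.

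Admission to a skilled facility is a listed secondary objective (Section 2.2.3), and nursing-home admission is part of the study hypothesis (Section 2.2.1). Section 5.8.4 uses the data three ways: cumulative incidence of first admission, a cause-specific Cox comparison of the CHARM risk groups, and a model for recurrent admissions. All three rest on this one item.

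**Working it through.** The point turns on wording, and the protocol states no figure to reproduce. The steps are as follows.

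**1. Is the endpoint definition consistent?** Not fully. The opening sentence of Section 3.2.4 places the stay outside the hospital; the later one counts a transfer inside it. The later sentence is worded as an extension and carries its own rationale, so the likely intent is to include these transfers. The opening sentence was not adjusted to match, and the item's hospital exclusion follows that opening sentence.

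**2. What does the item cover?**

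| Situation | Section 3.2.4 | Appendix 4 item |
|---|---|---|
| Nursing home | Event | Included by name |
| Free-standing acute or sub-acute rehabilitation | Event | Included by name |
| Regular hospital ward | Not an event | Excluded |
| Rehabilitation unit in the same hospital | Event | Rehabilitation clause suggests yes; hospital clause suggests no |

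Only the last row is unclear. There the two closing sentences of the item pull in opposite directions.

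**3. Is there another source?** None is described. Table 4.2.4 has no healthcare-team entry for facility admission, and the healthcare-team forms in Appendix 2 contain no such question. Section 2.6.8 lists GVHD, relapse, survival and day-100 organ toxicity as the post-transplant content taken from CIBMTR forms.

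**4. Would the study-chair route catch it?** Only when someone sees an ambiguity. Under Section 4.2.5 the central survey group collects the follow-up answers directly from subjects. An unsure answer could prompt a query; a plain no would not.

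**5. Could there be unprinted follow-up questions?** The Appendix 4 table gives a count of 1-3 items for this assessment, while one question is printed per time point. The same appendix says that it prints all the questions, and its counts are not reliable elsewhere: it gives 6 items for the IADL scale and prints 7. Unprinted questions cannot be excluded, but the document's own statement is against them.

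**6. How large could the effect be?** The shortfall in one-year incidence is

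shortfall = p × s × m

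where p is the true incidence, s the share of first admissions that are same-hospital transfers, and m the fraction of those subjects who answer no. The protocol gives none of the three. As assumptions for illustration only, take p from 0.10 to 0.20, s from 0.10 to 0.40 and m from 0 to 1. The simple binomial standard error is sqrt(p(1−p)/880), which ignores censoring and competing death.

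| p | s | SE | m = 0 | m = 0.5 | m = 1 |
|---|---|---|---|---|---|
| 0.10 | 0.10 | 0.0101 | 0 | 0.005 (0.5 SE) | 0.010 (1.0 SE) |
| 0.15 | 0.25 | 0.0120 | 0 | 0.019 (1.6 SE) | 0.0375 (3.1 SE) |
| 0.20 | 0.40 | 0.0135 | 0 | 0.040 (3.0 SE) | 0.080 (5.9 SE) |

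The result depends on m as much as on the other two inputs, and m is exactly what the wording leaves open. The table shows sensitivity; it is not an estimate.

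**The case against.** The strongest reply is that the item already names acute and sub-acute rehabilitation. A subject in an in-hospital rehabilitation unit can properly answer yes, the hospital exclusion can fairly be read as referring to ordinary wards, and unsure is available. This largely stands: it rules out any claim that these events are systematically lost. It does not remove the ambiguity, because the item never says which of its two clauses governs a unit inside the hospital.

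A reader might also infer that, since only some centres have such a unit, the comparison of CHARM groups is distorted. The protocol does not support that. The groups are tertiles of a patient-level score (Section 5.8), and nothing links a centre's facilities to its patients' scores. Under-reporting unrelated to the score would mainly lower the absolute incidence and the precision, with little effect on a hazard ratio if incidence is modest. Centre is not among the characteristics listed in Section 5.6 for adjustment, but that alone shows no bias.

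Two smaller complaints do not hold up. Footnote 3 of Table 4.2.4 is an open-ended list and does not conflict with Section 3.2.4. The missing mention of an overnight stay in the item has no shown practical effect, since it asks about being admitted.

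**Conclusion.** The mismatch is real and narrow. Section 3.2.4 is internally inconsistent about location, and the single described data source leaves unclear how to report a transfer that the section counts. Some events may be missed or coded inconsistently, which would lower the reported incidence of facility admission. The size cannot be estimated from the protocol and may be zero. The conclusion rests on two readings: that the later sentence of Section 3.2.4 states the intended definition, and that the printed question is the whole item, as the appendix says. It concerns one secondary endpoint; NRM, the sample size and the CHARM score are not affected. It is worth correcting because the correction is cheap.

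**What to change.** Reconcile the two sentences of Section 3.2.4, so that one statement says which stays count and treats units inside the treating hospital explicitly. If the later sentence is the intended rule, add a clause to the Appendix 4 item at all three follow-up times, along these lines: *Count an overnight stay in a rehabilitation unit inside the hospital where you were treated. Do not count stays on regular hospital wards.*

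The cost is one amended item with Spanish and Mandarin translations, and no extra visits. The downside is that answers collected before and after the change come from different wording. Recording the wording version with each response would let the analysis describe the two sets separately.
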